## 8.3 Adverse Events and Serious Adverse Events

### 8.3.1 Definition of Adverse Events (AE)

An Adverse Event (AE) is any unfavorable and unintended sign (including an abnormal laboratory finding), symptom, or disease temporally associated with the use of a medical treatment or procedure that may or may not be considered related to the medical treatment or procedure. An AE is a term that is a unique representation of a specific event used for medical documentation and scientific analyses.

### 8.3.2 Definition of Serious Adverse Event (SAE)

An adverse event (AE) or suspected adverse reaction is considered "serious" if, in the view of either the investigator or sponsor, it results in any of the following outcomes: death, a life-threatening adverse event, or prolongation of existing hospitalization, a persistent or significant incapacity or substantial disruption of the ability to conduct normal life functions. Important medical events may also be considered serious when they require medical or surgical intervention to prevent death, risk of permanent injury or disability, or prolonged hospitalization.

COVID-19 patients who require hospital admission are clinically expected to have adverse events related to their underlying condition and standard treatment, independent of any research intervention. Examples of common medical events in this population include (but are not limited to): respiratory failure requiring oxygen supplementation and/or intubation, ventilator associated pneumonia, venous thromboembolic disease, or encephalopathy, cytokine storm, shock requiring vasopressors and renal failure requiring renal replacement therapy.

Subjects may also incur AEs that could be expected to occur at higher rates because of the study intervention. These include medical events such as: serious allergic reactions (anaphylaxis or bronchospasm requiring treatment), transfusion related acute lung injury

(TRALI), transfusion associated circulatory overload (TACO) and transmission of infectious agents.

**Pre-existing medical conditions or unchanged, chronic medical conditions.** Pre-existing medical conditions or unchanged, chronic medical conditions are NOT considered AEs and should not be recorded on the AE case report form (CRF). These medical conditions should be adequately documented on the medical history and/or other source documents. In this trial, any medical conditions not present prior to randomization but that emerge after randomization are considered AEs.

**Exacerbation of Pre-existing medical conditions.** A pre-existing medical condition judged by the investigator to have worsened in severity or frequency or changed in character is considered an adverse event.

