## Study Population

Adults presenting to the emergency department (ED) with their first episode of symptomatic, laboratory-confirmed COVID-19 illness, who are at high risk for progression to severe/critical illness, but who are clinically stable for outpatient management at randomization.

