### 3.1 Primary Endpoint

*Operational definition of Hospitalization Care in the primary endpoint:*

- The endpoint is determined based on the order to admit the patient to an inpatient hospital bed (including admission to observation status). Patients may board in emergency departments or other outpatient areas awaiting inpatient beds for some time; therefore, the intent to place the patient in an inpatient bed is considered to be hospitalization. Observation in an emergency department observation unit would not count as hospitalization but only as emergency care. In the event that a patient worsens in the emergency department shortly after administration of the intervention and requires admission during that same visit, we will consider that that patient has met this primary endpoint.

*Operational definition of Emergency Care in the primary endpoint:*

- This endpoint is determined based on any presentation to an emergency department or urgent clinic for care. COVID-19 patients may be redirected to special areas adjacent to or outside of the usual emergency department for evaluation and treatment; therefore, the presentation for emergency or urgent care is considered the endpoint rather than physical entry into a specific area.

*Operational definition of Death in the primary endpoint:*

- Patients who die outside the hospital during the 15 days following randomization will meet this endpoint. Death notice or public records can confirm death.

*Justification of the primary endpoint:*

Hospitalization is a hard metric of meaningful worsening of disease.

- Hospitalization is a readily observable and objective outcome. It does not depend on self assessment, does not depend on return to the enrollment site, and can be verified by self-report, proxy-report, or even limited source documents from any admitting hospital or clinic. As such, it has low vulnerability to missing data or bias.
- The endpoint is a marker for worsening of disease. Hospitalization is a marker for the need of more intensive treatment that cannot be managed as an outpatient and is similar to the criteria used to characterize an adverse event as serious.
- The endpoint matters to patients. The need for hospitalization is a significant and meaningful event for patients. Hospitalization also removes patients from families and support systems further aggravating other symptoms of disease progression.

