## 8.2 Safety and Other Assessments

### 8.2.1 Safety Assessment

All adverse events (AEs) will be recorded until ED discharge. All AEs occurring until discharge from the emergency department must be reported in WebDCU™. After discharge from the emergency department and at each follow-up contact until the end of study, only serious adverse events will be reported in WebDCU and any event that leads to hospitalization or an ED or urgent care visit even if deemed non-serious. Investigators will also review medical records on Day 30 for any serious adverse events.

Subjects will be monitored for the following plasma-specific AEs:

- Transfusion reactions: fever, rash, itching
- Serious allergic reactions (anaphylaxis or bronchospasm requiring treatment)
- Transfusion Associated Acute Lung Injury (TRALI), as defined by <https://www.ncbi.nlm.nih.gov/pmc/articles/PMC6850655/> (21). Given that these are patients with other risk factors for ARDS, a diagnosis of "possible TRALI" will require stable respiratory status in the 12 hours before transfusion. Because TRALI may mimic the natural progression of COVID-19, the demonstration of HLA antibodies in the donor product that matches the recipient's HLA type will also be necessary to make the diagnosis of "possible TRALI".
- Transfusion Associated Circulatory Overload (TACO)

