### 8.3.5 Time Period and Frequency for Event Assessment and Follow-up

The occurrence of an adverse event (AE) or serious adverse event (SAE) may come to the attention of study personnel during study visits and interviews of a study participant presenting for medical care, or upon review by an independent medical safety monitor (section 10.4).

Adverse events will be captured and reported in WebDCU™. Information to be collected includes time of onset, clinician's assessment of severity, relatedness to study intervention, and time of resolution/stabilization of the event. All SAEs will also include a narrative of the event with additional testing results if conducted. All AEs occurring until discharge from the emergency department must be reported in WebDCU™. After discharge from the emergency department, only serious adverse events will be reported in WebDCU™. All AEs will be followed to adequate resolution/stabilization or subject end of study.

All non-serious AEs must be recorded on the electronic AE CRF within 5 days from the time it was discovered by the site study personnel. For SAEs, the data entry must take place within 24 hours of discovery of the event. Upon submission of an SAE, the system will trigger an automatic email notification to the Independent Medical Safety Monitor (iMSM) stating that an SAE has occurred. The iMSM will access the information via the password protected web

based system and will review the SAE data within 2 business days of being notified for completeness of reporting, and will enter their assessment of relatedness and expectedness. Expedited reporting to the DSMB and regulatory parties will occur for all potentially related unexpected SAEs. The reporting timeline will follow FDA requirements: within 7 calendar days of the sponsor's knowledge of an unexpected fatal or life-threatening event; within 15 calendar days for all other unexpected potentially related SAEs.

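### The SAE definition omits new hospital admission in an outpatient trial, so a complication that leads to admission can be handled as a non-serious event

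*Combined protocol and SAP*

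**What the plan says.** Section 8.3.2 defines an event as serious if, in the investigator's or sponsor's view, it results in "death, a life-threatening adverse event, or prolongation of existing hospitalization, a persistent or significant incapacity" or a substantial disruption of normal life functions. A further sentence is permissive: "Important medical events may also be considered serious when they require medical or surgical intervention to prevent death, risk of permanent injury or disability, or". The item that closes that sentence is again a stay that is prolonged. Neither sentence mentions a first admission.

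Participants are "clinically stable for outpatient management at randomization" (section 1.2, Study Population). In justifying the primary endpoint, section 3.1 says that hospitalization "is similar to the criteria used to characterize an adverse event as serious".

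Two sections govern reporting after the participant leaves the emergency department (ED). Section 8.2.1 requires SAEs and also "any event that leads to hospitalization or an ED or urgent care visit even if deemed non-serious". Section 8.3.5 says "After discharge from the emergency department, only serious adverse events will be reported in WebDCU".

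Section 8.3.5 also sets the timing: "For SAEs, the data entry must take place within 24 hours of discovery of the event", against "All non-serious AEs must be recorded on the electronic AE CRF within 5 days" for the rest. A narrative is required for all SAEs. Submitting an SAE triggers the automatic email to the independent medical safety monitor, who then has 2 business days to review it.

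**The concern.** The only hospital-related outcome in the list presupposes that the person is already in hospital. Here almost nobody is, so the criterion is close to empty. The event one would most want it to catch is a participant who goes home after the infusion and is then admitted, and that is a new admission. The same applies to a participant who worsens in the ED after infusion and is admitted during that visit, a case that section 3.1 foresees.

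Safety is part of the primary objective (sections 1.1 and 1.2). The recognised harms of plasma named in section 8.3.2 include circulatory overload (TACO), lung injury (TRALI) and serious allergic reaction. Any of these can lead to admission without being judged life-threatening. Whether such an event counts as serious then rests on local judgement across at least 30 sites, with care teams who know the assignment (sections 5.4 and 6.1.3). SAE counts could differ between sites, and possibly between arms, for reasons unrelated to the product.

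**Working it through.** No stated figure depends on this definition, so the check is mainly textual, with one calculation for scale.

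**1. Is new admission a seriousness criterion?** Section 8.3.2 does not list it. There is an 'or' in the middle of the list, just before the item on prolonged stay, which suggests that a preceding item was lost. Section 3.1, which likens hospitalization to a seriousness criterion, points the same way. No section says that admission was left out on purpose, for example because it is an endpoint component.

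**2. Which other routes could make such an admission serious?** There are three:
- The life-threatening criterion, for severe cases.
- The criterion on incapacity or disruption of normal life, which is a matter of judgement.
- The important-medical-event sentence, which says events may be considered serious and whose hospital item is again a prolonged stay.

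None of these makes admission serious in itself.

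**3. What happens to an admission classed as non-serious?**
- Entry: under 8.2.1 it is entered. The words on events deemed non-serious confirm that the protocol accepts an admission can be so classed.
- Timing: 5 days from discovery, instead of 24 hours.
- Monitor: no automatic alert and no 2-business-day clock, since both start from an SAE submission.
- Narrative: not required.
- Tabulation: missing from SAE counts by arm.

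**4. Do 8.2.1 and 8.3.5 agree?** No. The first requires non-serious events leading to hospital, ED or urgent care to be reported. The second limits post-discharge reporting to SAEs. The amendment history (section 11) shows that Version 3 added the wider wording to 8.2.1, so 8.3.5 was most likely not updated to match.

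**5. Scale.** Inputs are from section 2.3.1 (expanded-access programme, 5000 transfusions) and section 1.1 (450 per arm).
- Related events: 4 deaths + 11 TACO + 7 TRALI + 3 allergic = 25, and 25/5000 = 0.50%, which reproduces the protocol's figure.
- The deaths are set aside because death is already a criterion: 11 + 7 + 3 = 21, and 21/5000 = 0.42%.
- Expected in 450 plasma recipients: 450 × 0.0042 = 1.89, about 1.9.
- Probability of at least one: 1 − (1 − 0.0042)^450 = 0.85.
- At the original 300 per arm: 300 × 0.0042 = 1.26, with probability 0.72.

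These rates come from patients with moderate to severe disease, so applying them here is an assumption. The 1.9 is also a count of all such events. Only those that lead to admission and meet no other seriousness criterion fall in the gap.

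**The case against.** The strongest reply is that little is actually lost. Section 8.2.1 still puts these events in the database, and all AEs up to ED discharge are recorded, including those in the observation of at least 1 hour after infusion. Admission for any reason within 15 days counts in the primary endpoint (section 8.1.1). Hospital-free days and worst severity run to day 30 (section 8.1.2), so an excess of admissions on plasma would be visible. Severe overload, lung injury or anaphylaxis would often qualify as life-threatening. The reference in 8.2.1 to events deemed non-serious may even mean that admission was deliberately not made an automatic criterion.

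Much of this stands, and it rules out several stronger readings that a reader might infer:
- **That the events escape expedited reporting.** Section 8.3.5 expedites only SAEs that are potentially related and unexpected. Section 8.3.2 names TACO, TRALI and serious allergic reaction among events that could be expected from the intervention, so they might not be expedited even if classed as SAEs.
- **That they escape all independent review.** Section 10.4 describes ongoing review by the safety monitor of data entered by the sites. What is lost is the prompt alert and the review deadline.
- **That they are not reported at all.** This holds only if 8.3.5 is read alone, and the amendment history shows that capture was intended.
- **That every admission measures the problem.** Most admissions would presumably be COVID-19 progression, and the documents give no separate admission rate.

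The reply does not restore admission as a criterion. The efficacy endpoints count admissions whatever the cause, so they cannot separate a transfusion complication from progression. If the omission was deliberate, the protocol does not say so, and section 3.1 sits awkwardly with it.

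**Conclusion.** The concern holds as a gap in definition and routing. As written, a post-infusion complication that leads to a new admission can be classed as non-serious. It would then be handled on the slower route, without the monitor alert, review deadline or narrative, and left out of SAE counts by arm. Sections 8.2.1 and 8.3.5 also contradict each other.

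The number of events affected is probably small: some fraction of about 1.9 expected in 450 recipients, on the assumption that the cited expanded-access rates carry over. With so few expected, one event classed differently could still change the safety picture. Sample size, power and the efficacy analysis are unaffected. This should be corrected because the change is cheap and safety is a primary objective.

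**What to change.** - In section 8.3.2, insert 'inpatient hospitalization or' immediately before the item on prolonged stay.
- If admissions for COVID-19 progression are to be exempt from SAE handling because they are endpoint events, state that exception explicitly. Keep admissions with a possible transfusion cause in the SAE route.
- Bring section 8.3.5 into line with section 8.2.1 on what is reported after ED discharge.

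The cost is a short protocol amendment and a modest number of extra SAE forms and monitor reviews. An explicit exception for progression would limit that number.

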### 8.3.3 Classification of an Adverse Event

For adverse events (AEs) not included in the protocol defined grading system, the severity of adverse events will be determined referencing the National Cancer Institute (NCI) Common Terminology Criteria for Adverse Events Version 5.0 (CTCAE). The CTCAE provides a grading (severity) scale for AEs with unique clinical descriptions of severity based on this general guidance:

Grade 1: Mild AE

Grade 2: Moderate AE

Grade 3: Severe AE

Grade 4: Life-Threatening or Disabling AE

Grade 5: Death related to AE

### 8.3.4 Relationship to Study Intervention

Adverse reaction is different from an adverse event. Suspected adverse reaction means any adverse event for which there is a reasonable possibility that the study intervention caused the adverse event. For the purposes of IND safety reporting, 'reasonable possibility' means there is evidence to suggest a causal relationship between the study intervention and the adverse event. A suspected adverse reaction implies a lesser degree of certainty about causality than adverse reaction, which means an adverse event is definitely caused by the study intervention.

Per FDA guidance a suspected adverse reaction is one that is known to be strongly associated with the study intervention, or one that is very uncommon in the study population, or one shown in aggregate analysis to occur more frequently in the treatment group. Generally anticipated adverse events are not suspected adverse reactions.

Because 'reasonable possibility' can be difficult to determine, this trial uses an algorithmic approach to describing relatedness.

#### Algorithm to Determine Relatedness of Adverse Event to Study Agent

Not Related	The temporal relationship between treatment exposure and the adverse event is unreasonable or incompatible and/or adverse event is clearly due to extraneous causes (e.g., underlying disease, environment)
Unlikely	Must have both of the following 2 conditions, but may have reasonable or only tenuous temporal relationship to intervention. 
 
• Could readily have been produced by the subject's clinical state, or environmental or other interventions.
 
• Does not follow a known pattern of response to intervention.
 

Reasonable Possibility	Must have at least 2 of the following 3 conditions 
 
• Has a reasonable temporal relationship to intervention.
 
• Could not readily have been produced by the subject's clinical state or environmental or other interventions.
 
• Follows a known pattern of response to intervention.
 

Definitely	Must have all 3 of the following conditions 
 
• Has a reasonable temporal relationship to intervention.
 
• Could not possibly have been produced by the subject's clinical state or have been due to environmental or other interventions.
 
• Follows a known pattern of response to intervention.
 

### 8.3.5 Time Period and Frequency for Event Assessment and Follow-up

The occurrence of an adverse event (AE) or serious adverse event (SAE) may come to the attention of study personnel during study visits and interviews of a study participant presenting for medical care, or upon review by an independent medical safety monitor (section 10.4).

Adverse events will be captured and reported in WebDCU™. Information to be collected includes time of onset, clinician's assessment of severity, relatedness to study intervention, and time of resolution/stabilization of the event. All SAEs will also include a narrative of the event with additional testing results if conducted. All AEs occurring until discharge from the emergency department must be reported in WebDCU™. After discharge from the emergency department, only serious adverse events will be reported in WebDCU™. All AEs will be followed to adequate resolution/stabilization or subject end of study.

All non-serious AEs must be recorded on the electronic AE CRF within 5 days from the time it was discovered by the site study personnel. For SAEs, the data entry must take place within 24 hours of discovery of the event. Upon submission of an SAE, the system will trigger an automatic email notification to the Independent Medical Safety Monitor (iMSM) stating that an SAE has occurred. The iMSM will access the information via the password protected web

based system and will review the SAE data within 2 business days of being notified for completeness of reporting, and will enter their assessment of relatedness and expectedness. Expedited reporting to the DSMB and regulatory parties will occur for all potentially related unexpected SAEs. The reporting timeline will follow FDA requirements: within 7 calendar days of the sponsor's knowledge of an unexpected fatal or life-threatening event; within 15 calendar days for all other unexpected potentially related SAEs.

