### 1.4 Schedule of Activities

	Study Day										
	0	2	4	6	8	10	12	14	15	30	
Inclusion/Exclusion											
Informed Consent	X										
Demographics	X										
Medical History	X										
Contact Information	X										
ABO type	X										
Randomization	X										
Pre-intervention research blood draw	X										
Administer CP or Placebo											
Post-intervention research blood draw	X										
X											
Research Blood Draw									X	X	
Residual viral media / saliva sample	X										
Assess for Hospitalization		X	X	X	X	X	X	X	X	X	
Vital Status		X	X	X	X	X	X	X	X	X	
Symptom Inventory	X	X	X	X	X	X	X	X	X	X	

Adverse Event Assessment	X	X	X	X	X	X	X	X	X
Review Electronic Medical Record / Death Index	X								X X X

*Study Day 0 is the same as the day of randomization. Day 0 starts from the time of randomization until 23:59 of that calendar day. Day 1 begins at 00:00 on the following day.*

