**1.5.2.8 Day 15**

- Collect blood sample for antibody testing

Telephone, remote, or in-person assessment of

- Hospitalization, urgent medical visits, and vital status
- Any adverse event
- Symptoms
- Blinding to intervention arm

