**1.5.2.9 Day 30**

- Collect blood sample for antibody testing

Telephone, remote, or in-person assessment of

- Hospitalization, urgent medical visits, and vital status
- Any serious adverse event
- Symptoms

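### Sections 8.2.1 and 8.3.5 contradict each other on which adverse events are entered after emergency department discharge, so non-serious visit-related events may be under-reported and not comparable across sites

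*Combined protocol and SAP*

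**What the plan says.** Up to discharge from the emergency department (ED) there is no conflict. Section 8.3.5 says "All AEs occurring until discharge from the emergency department must be reported in WebDCU", and 8.2.1 says the same.

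After discharge the two sections differ:

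- **Section 8.2.1 (Safety Assessment):** "only serious adverse events will be reported in WebDCU and any event that leads to hospitalization or an ED or urgent care visit", with the qualifier that this holds even for events judged non-serious. The rule runs to the end of the study.
- **Section 8.3.5 (Time Period and Frequency):** "After discharge from the emergency department, only serious adverse events will be reported in WebDCU". There is no added category.

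Three other places bear on this:

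- **Section 8.3.2** defines a serious adverse event (SAE) by outcomes that include "death, a life-threatening adverse event, or prolongation of existing hospitalization". A new admission is not listed as a criterion in its own right.
- **Section 1.5.2.8 (Day 15)** lists "Any adverse event", while **Section 1.5.2.9 (Day 30)** lists "Any serious adverse event".
- **Section 8.3.5** also names what an adverse event report contains (onset, severity, relatedness, resolution) and sets the entry deadlines: 5 days for non-serious events and 24 hours for SAEs.

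**The concern.** A site cannot satisfy both sentences. Under 8.2.1, a participant who returns to an ED with a non-serious problem generates an adverse event report. Under 8.3.5, the same participant does not.

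What is at stake is the safety record of such visits. Section 8.1.1 counts an unscheduled ED or urgent care visit as a primary event, and an admission for whatever reason likewise. Section 8.2.1 lists fever, rash and itching among the plasma reactions to be monitored, and Section 1.5 sets observation after infusion at a minimum of one hour. A return visit for a late, mild reaction would therefore count as disease progression. The adverse event report is where the protocol provides for someone to judge whether plasma caused it. If sites apply different rules, adverse event counts are too low at some sites and cannot be compared across sites. Those counts go to the monitoring board, which receives safety data at each interim look (9.2.2) and weighs the safety profile when considering a larger sample (9.1).

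**Working it through.** **Side-by-side reading.** The plan states no figure on this point, so the check is a comparison of current text.

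| Event | 8.2.1 | 8.3.5 |
|---|---|---|
| Any adverse event before ED discharge | report | report |
| SAE after discharge | report | report |
| Non-serious event after discharge leading to an ED or urgent care visit | report | do not report |
| Admission after discharge that meets no 8.3.2 criterion | report | do not report |
| Other non-serious event after discharge | do not report | do not report |

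The sections part in rows three and four. Row four exists only because 8.3.2 omits new admission. Its clause on important medical events may capture some admissions, but only by judgement. The Day 15 item, read as a reporting rule, would also take in row five and so agrees with neither section.

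The amendment history suggests how this arose. Version 3 added the visit category to 8.2.1, and no entry shows a matching change to 8.3.5. Version 3 also removed the any-adverse-event item from the telephone contacts on Days 2 to 14, but Day 15 kept it. The contradiction is between passages now in force; the log only explains it.

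**Size of the affected class.** Inputs: 450 per arm (1.2, revised maximum); a 20% control proportion and a 10-point reduction, hence 10% on plasma (9.1, illustrative example).

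- Control: 450 × 0.20 = 90
- Plasma: 450 × 0.10 = 45
- Total with a Day 15 primary event: 90 + 45 = 135

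This total includes deaths and events that are serious under either rule. Only the non-serious share *s* is in dispute, and the documents do not give it. Participants affected = 135 × *s*:

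| Assumed *s* | Control | Plasma | Total |
|---|---|---|---|
| 10% | 9 | 4.5 | 13.5 |
| 25% | 22.5 | 11.25 | 33.75 |
| 50% | 45 | 22.5 | 67.5 |
| 75% | 67.5 | 33.75 | 101.25 |

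At the original 300 per arm, the class is 60 + 30 = 90, and the same shares give 9 to 67.5 participants.

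**Effect on the arm comparison.** Take *s* = 50%, equal in both arms. If every site follows 8.2.1, participants with a reported event number 90 and 45, a difference of 45/450 = 10 points. If every site follows 8.3.5, they number 45 and 22.5, a difference of 22.5/450 = 5 points. The ratio is 2 in both cases. The choice of rule changes the counts and the absolute difference, but under this assumption not the ratio.

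**The case against.** The strongest reply is that the wording conflict is real but its consequences are small, and much of that reply stands.

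- **Arm bias.** A reader might infer that the plasma-versus-placebo safety comparison is biased. The documents do not show this. Site is in the randomization scheme (6.3), so a site's choice of rule should fall on both arms alike. Site coordinators may become unblinded (4.2), but nothing indicates that they would choose a rule case by case. Mild plasma reactions would fall in the plasma arm, but no rate is given for those appearing after discharge and prompting a visit.
- **Loss of all admissions.** A reader might infer that 8.3.5 removes every hospital admission. That is too strong. Section 8.3.2 leaves seriousness to the investigator or sponsor, and Section 3.1 likens hospitalization to the seriousness criteria. Some admissions might go unreported; no more can be said.
- **No other record.** The site team collects data on all admissions and visits (1.5) and reviews records at Day 30 (1.5.3). The documents do not describe the fields of those forms, so it cannot be said that relatedness is recorded nowhere else. Section 8.3.5 does, however, specify these assessments for adverse event reports.
- **Which rule sites follow.** The deadlines in 8.3.5 do not make it controlling; 8.2.1 is the more specific text. Central data review and monitoring of adverse event completeness (10.4) may limit divergence, but reviewers would need one rule to check against.
- **Schedule of activities.** The "Adverse Event Assessment" row shows assessment, not reporting, and is no further contradiction. The Day 15 item can be read the same way and is probably a leftover, so it is a secondary point.

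**Conclusion.** The point holds as an internal contradiction with a limited consequence. Two current sections give incompatible rules for one class of events: those after discharge that are not classed as serious but lead to a hospital, ED or urgent care visit. A site following 8.3.5 would omit their adverse event reports, so counts could be too low and not comparable across sites.

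Efficacy is unaffected because the primary endpoint is collected separately (1.5, 8.1.1). Events clearly serious under 8.3.2 and events before discharge are treated alike in both sections.

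The figure of 135 should not be read as the number of lost reports. It is the whole class of expected Day 15 primary events, deaths included. The discrepancy is its non-serious part: about 14 to 101 participants for an assumed share of 10% to 75%. Even that is reached only if every site follows 8.3.5. The range also rests on an event-rate example written for 600 participants, whereas the plan's stated reason for enlarging the sample is an event rate above the one assumed (9.1). Events on Days 16 to 30 would be additional. The point should be corrected, but it does not threaten the trial's main conclusion.

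**What to change.** 1. In 8.3.5, replace the sentence on post-discharge reporting with the rule that 8.2.1 has carried since version 3, running to the end of the study. The 5-day entry deadline for non-serious events already in 8.3.5 can serve the added category.
2. Bring the Day 15 item in 1.5.2.8 into line with that rule, or state that it concerns what is asked and not what is entered.
3. Reconcile 8.3.2 with it by stating whether a new hospitalization is in itself a seriousness criterion. If the sponsor decides that it is, admissions also come under the 24-hour entry and safety monitor review in 8.3.5.
4. Send sites a memo stating the single rule.

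The cost is protocol wording and the memo. Steps 1 and 2 need no data collection beyond what 8.2.1 already requires.
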